#### **6.6. Baseline Definition**

The Baseline value will be defined as the Visit 3 (Day 1) measurement. If this measurement is not available, the Visit 1 (D-28 to D-15) measurement will be used as the baseline value. Table 4 below contains a list of definitions of PD parameters and baseline of parameters covered in this SAP.

**Table 4: Baseline**

Parameter	Definition	Baseline
Peak FEV 1	Maximum FEV 1 over the period of 12 hours post-morning dose.	Average of the pre-dose FEV 1 measured at -45 minutes and -15 minutes at Day 1
Trough FEV 1	Mean FEV 1 obtained 23 hours 15 minutes and 23 hours 45 minutes post-morning dose of the previous day.	Average of the pre-dose FEV 1 measured at -45 minutes and -15 minutes at Day 1
Time-normalized Area Under the Curve FEV 1		Average of the pre-dose FEV 1 measured at -45 minutes and -15 minutes at Day 1
FVC	Amount of air which can be forcibly exhaled from the lungs after taking the deepest breath possible  Mean FVC obtained 23 hours 15 minutes and 23 hours 45 minutes post-morning dose of the previous day.	The baseline assessment is the average of the pre-dose FVC measured at -45 minutes and -15 minutes at Day 1
Laboratory Parameters (hematology, blood chemistry, liver function and urinalysis)		Screening (Day -28 to Day -15).
Vital Signs		Day 1 (1hr pre-dose)

Parameter	Definition	Baseline
ECG		Day 1 (pre-dose)
Physical Examinations		Day -1

## 6.7. Derived and Transformed Data

### 6.7.1. Age

Age is the subject's age in complete years – calculated based on the informed consent date and subject's date of birth.

If the month and day of informed consent is on or after the month and day of birth:

$$\text{Age} = \text{year of informed consent} - \text{year of birth}$$

If the month and day of informed consent is before the month and day of birth:

$$\text{Age} = \text{year of informed consent} - \text{year of birth} - 1$$

### 6.7.2. Study Day

If the date of interest occurs on or after the randomization date:

$$\text{Study day} = \text{date of interest} - \text{randomization date} + 1$$

If the date of interest occurs before the randomization date:

$$\text{Study day} = \text{date of interest} - \text{randomization date}$$

There is no study day 0.

### 6.7.3. Change from Baseline

Change from baseline will be calculated by subtracting the baseline measurement from the post baseline measurement.

Change from baseline = post baseline measurement – baseline measurement.

### 6.7.4. Visits

Table 5 contains a list of visits in the study period. Data will be analyzed based on the nominal visit/time.

**Table 5: Visits (Days)**

Visit	Scheduled Day	Days
Visit 1 (Screening)	-15	-28 to -15
Visit 2 (Run-in)	-14	-14 to -2

Visit 3 (Baseline)	1	-1 to 2*
Visit 4 (Week 1)	7	
Visit 5 (Week 2)	14	
Visit 6 (Week 3)	21	20 to 22*
Visit 7 (Follow-up)	35	33 to 37

\*: Subjects will stay in the clinic as in-patients for about 36 to 48 hours at Visit 3 and Visit 6.

### 6.7.5. Unscheduled Assessments

Unscheduled assessments (laboratory data, ECG or vital signs associated with non-protocol clinical visits or obtained in the course of investigating or managing adverse events) will be included in listings, but not in summaries. If more than one assessment is available for a given visit, the first or most valid observation will be used in summaries presented in listings and other assessments will be classed as unscheduled measurement.

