#### **4.5. Clinical Assessments**

The following clinical assessments will be performed during the study.

1. Vital signs: vital signs will be taken at screening (Day -28 to -15), Day -1, Day 1 (1 hour pre-dose and 1 hour post-dose), Day 2, Day 7, Day 14 (1 hour pre-dose and 1 hour post-dose), Day 20, Day 21 (post-dose), Day 22 (ie 24 hours after Day 21 dose), and Day 35 ( $\pm 2$ ; ie 2 weeks follow-up after last dose date).
2. Physical Examination: physical examination will be performed at screening (Day -28 to Day -15 (comprehensive physical examination)), Day -1 (ie, 24 hours before Day 1 dose), Day 7 (pre-dose), Day 14 (pre-dose), and Day 20 (pre-dose).
3. 12 Lead Electrocardiogram (ECG): 12 lead ECG will be performed at screening (Day -28 to Day -15), Day 1 (pre-dose) and Day 21 (pre-dose).
4. Laboratory Tests: hematology, biochemistry, and urine analysis tests will be performed at screening (Day -28 to Day -15), Day 7 (pre-dose), Day 14 (pre-dose), Day 21 (pre-dose), and Day 35 ( $\pm 2$ ; ie 2 weeks follow-up after last dose date). Urine analysis for drugs of abuse and cotinine and blood alcohol tests will be performed on screening (Day -28 to Day -15), Day -1, and Day 20 (pre-dose). Serum pregnancy testing will be performed in all female subjects on screening (Day -28 to Day -15), and urine pregnancy testing will be performed in female subjects on Day -1 and Day 35 ( $\pm 2$ ).
5. Other safety assessments consisting of monitoring and recording all Adverse Events, serious adverse events (SAEs) and Concomitant Medications will be collected throughout the study.
6. Pharmacodynamics: The spirometry test will be performed at screening (Day -28 to Day -15), Day 1 (pre-dose -45 mins and -15 mins), Day 7 (pre-dose -45 mins and -15 mins), Day 14 (pre-dose -45 mins and -15 mins), Day 21 (pre-dose -45 mins and -15 mins), and Day 22 (ie 24 hours after Day 21 dose). Pre-dose FEV1 and FVC will be assessed at -45 minutes and -15 minutes prior to dosing on Day 1, Day 7, Day 14, and Day 21. Trough FEV1 will be assessed on Day 22 (ie 24 hours after Day 21 dose). On Day 1 and Day 21,

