## **6. GENERAL CONSIDERATIONS FOR DATA ANALYSES AND HANDLING**

### **6.1. General Summary Table and Individual Subject Data Listing Consideration**

In general, listings will be sorted and presented by treatment and subject number. Subject number when broken down consists of the site number and 4 digits sequential number. Study visits will be labeled as Screening, Baseline (Day 1), Day 2, Day 7, Day 14, Day 20 and Day 21 as well as End of Study (Follow Up) and Unscheduled. When required, the time of the scheduled assessment will be included.

The following treatment levels will be used for all tables, figures, and listings in the order below. Spiriva R will be used for Spiriva® Respimat® in tables, figures and listings for simplicity.

GSP304 [REDACTED]
GSP304 [REDACTED]
GSP304 [REDACTED]
GSP304 Total (AE/SAE-related tables)
GSP304 Placebo
Spiriva R 5 µg

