#### **10.4. Laboratory Data**

Baseline and post-baseline clinical laboratory data (hematology, biochemistry, liver function, and urinalysis), will be summarized for Visit 4 to Visit 7 (the Final Visit). Descriptive statistics (number of subjects, mean, SD, median, minimum and maximum) will be presented for laboratory data as well as change from baseline by treatment and visit. In addition, values outside the respective normal range and values deemed as clinically significant by the Investigator will be listed.

The number of subjects with values of potential clinical significance determined by the investigator will be tabulated by treatment group and visit.

Shift tables will present changes from baseline in laboratory data (categorized as normal; abnormal, not clinically significant; and abnormal, clinically significant) to end of treatment.

All laboratory data will be listed by treatment and subject.

Estimated Glomerular filtration rate (eGFR) will be estimated using the Cockcroft-Gault approach.

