Footnote: [1] Pre-dose = within 1 hour before study drug administration in the morning (prior to pre-dose spirometry and PK procedure) on Day 1 (Baseline) and Day 14; Post-dose = within 1 hour after study drug administration in the morning; on Day 1 and Day 21; Trough = approximately 24 hours after study drug administration in the morning on Day 1

Table 14.3.6.4 Summary of Electrocardiogram Results

Panel/Parameter: <Parameter> (<Units>)

Parameter= Heart Rate (beats/minute), PR(msec), QRS(msec), QTcB(msec), QTcF(msec)

Footnote: [1] Baseline = Day 1 (pre-dose); N = Number of safety subjects;n = Number of subjects with data in the summarized category

Table 14.3.5.1.2  
 Shift Summary from Baseline to Day 21 in Biochemistry

Safety Set

Panel/Treatment Group/Parameter: <Placebo>(<N=xxx>); < Parameter> (<Units>)

Baseline [1]	Number of Subjects			Subject Status at Day 21			
	Baseline	Day 21	Day 21 and Baseline	Normal	Abnormal	ANCS	ACS
	N 1	N 2	N 3	n/N 3 (%)	n/N 3 (%)	n/N 3 (%)	n/N 3 (%)
Total	xx	xx	yy	xx/yy (xx.x) [2]	xx/yy (xx.x)	xx/yy (xx.x)	xx/yy (xx.x)
Normal	xx	xx	yy	xx/yy (xx.x) [3]	xx/yy (xx.x)	xx/yy (xx.x)	xx/yy (xx.x)
Abnormal	xx	xx	yy	xx/yy (xx.x) [4]	xx/yy (xx.x)	xx/yy (xx.x)	xx/yy (xx.x)
ANCS	xx	xx	yy	xx/yy (xx.x)	xx/yy (xx.x)	xx/yy (xx.x)	xx/yy (xx.x)
ACS	xx	xx	yy	xx/yy (xx.x)	xx/yy (xx.x)	xx/yy (xx.x)	xx/yy (xx.x)

[1] Baseline: Screening (Day -28 to Day -15); N1 = Number of safety subjects with baseline data; N2 = Number of safety subjects with Day 21 data; N3 = Number of safety subjects with baseline and Day 21 data; n = Number of subjects with data in the summarized category

Percentages are based on the number of subjects with a non-missing measurement for that variable in each corresponding visit.

[2] Percentages are based on total subjects with baseline and Day 21 data

[3] Percentages are based on subjects with normal status at baseline that have Day 21 data

[4] Percentages are based on subjects with abnormal status at baseline that have Day 21 data; similar for ANCS, ACS.

ANCS = Abnormal, not clinically significant; ACS = Abnormal, clinically significant

program location/program name.sas/ddmmmyyyy/hh:mm

Source Data: Listing xxxxxxx Database Extract Date: ddmmmyyyy

Programming notes:

For each laboratory parameter, subjects are included only once,  
 in the maximum post-baseline severity, for that laboratory parameter.

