3xULN elevations	xx (xx.x)	xx (xx.x)	xx (xx.x)	xx (xx.x)	xx (xx.x)	xx (xx.x)	xx (xx.x)
5xULN elevations	xx (xx.x)	xx (xx.x)	xx (xx.x)	xx (xx.x)	xx (xx.x)	xx (xx.x)	xx (xx.x)
10xULN elevations	xx (xx.x)	xx (xx.x)	xx (xx.x)	xx (xx.x)	xx (xx.x)	xx (xx.x)	xx (xx.x)
Gamma-glutamyl transferase							
2xULN elevations	xx (xx.x)	xx (xx.x)	xx (xx.x)	xx (xx.x)	xx (xx.x)	xx (xx.x)	xx (xx.x)
3xULN elevations	xx (xx.x)	xx (xx.x)	xx (xx.x)	xx (xx.x)	xx (xx.x)	xx (xx.x)	xx (xx.x)
5xULN elevations	xx (xx.x)	xx (xx.x)	xx (xx.x)	xx (xx.x)	xx (xx.x)	xx (xx.x)	xx (xx.x)
10xULN elevations	xx (xx.x)	xx (xx.x)	xx (xx.x)	xx (xx.x)	xx (xx.x)	xx (xx.x)	xx (xx.x)
Alkaline Phosphatase							
2xULN elevations	xx (xx.x)	xx (xx.x)	xx (xx.x)	xx (xx.x)	xx (xx.x)	xx (xx.x)	xx (xx.x)
3xULN elevations	xx (xx.x)	xx (xx.x)	xx (xx.x)	xx (xx.x)	xx (xx.x)	xx (xx.x)	xx (xx.x)
5xULN elevations	xx (xx.x)	xx (xx.x)	xx (xx.x)	xx (xx.x)	xx (xx.x)	xx (xx.x)	xx (xx.x)
10xULN elevations	xx (xx.x)	xx (xx.x)	xx (xx.x)	xx (xx.x)	xx (xx.x)	xx (xx.x)	xx (xx.x)
Total Bilirubin							
2xULN elevations	xx (xx.x)	xx (xx.x)	xx (xx.x)	xx (xx.x)	xx (xx.x)	xx (xx.x)	xx (xx.x)
3xULN elevations	xx (xx.x)	xx (xx.x)	xx (xx.x)	xx (xx.x)	xx (xx.x)	xx (xx.x)	xx (xx.x)
5xULN elevations	xx (xx.x)	xx (xx.x)	xx (xx.x)	xx (xx.x)	xx (xx.x)	xx (xx.x)	xx (xx.x)
10xULN elevations	xx (xx.x)	xx (xx.x)	xx (xx.x)	xx (xx.x)	xx (xx.x)	xx (xx.x)	xx (xx.x)

Direct Bilirubin

2xULN elevations	xx (xx.x)						
3xULN elevations	xx (xx.x)						
5xULN elevations	xx (xx.x)						
10xULN elevations	xx (xx.x)						

---

[1] Hy's Law criteria are based on the following:  $\geq 2$  x ULN elevation of Bilirubin and 3 x ULN elevation of either ALT or AST. In order to meet the above criteria, a subject must experience the elevation in bilirubin and ALT or AST at the same visit. N = Number of safety subjects; n = Number of subjects with data in the summarized category

Program location/program name.sas/ddmmmyyyy/hh:mm

Source Data: Listing xxxxxxx Database Extract Date: ddmmmyyyy

---

Programming notes:

---

Table 14.3.6.7  
 Summary of Physical Examination by Treatment

Safety Set

Panel/Parameter: <Parameter>

Visit	Category	GSP304				Spiriva R		
		(N=xxx) n (%)	(N=xxx) n (%)	(N=xxx) n (%)	Total (N=xxx) n (%)	Placebo (N=xxx) n (%)	5 ug (N=xxx) n (%)	Total (N=xxx) n (%)
Baseline[1]	n	xxx	xxx	xxx	xxx	xxx	xxx	xxx
	Normal	xx (xx.x)	xx (xx.x)	xx (xx.x)	xx (xx.x)	xx (xx.x)	xx (xx.x)	xx (xx.x)

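### Section 6.7.5 bars unscheduled and repeat laboratory, ECG and vital-sign values from every summary of those data, with no exception for the liver/Hy's Law table or the counts of potentially clinically significant values

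*SAP*

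**What the plan says.** Section 6.7.5 (Unscheduled Assessments) covers laboratory data, ECG and vital signs from visits outside the protocol or "obtained in the course of investigating or managing adverse events) will be included in listings, but not in summaries". For several values at one visit it adds that "the first or most valid observation will be used in summaries presented in listings and other assessments will be classed as unscheduled measurement". So a confirmatory repeat also becomes unscheduled and leaves the summaries.

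Section 10.4 plans the laboratory count: "The number of subjects with values of potential clinical significance determined by the investigator will be tabulated by treatment group and visit". Sections 10.5 and 10.6 say the same for vital signs and ECG.

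Table 14.3.5.4 counts subjects with liver-test elevations of 2, 3, 5 and 10 times the upper limit of normal (ULN), and subjects meeting Hy's Law. Its footnote states that "a subject must experience the elevation in bilirubin and ALT or AST at the same visit".

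Section 4.5 sets the schedule. After the screening baseline, laboratory tests fall on "Day 7 (pre-dose), Day 14 (pre-dose), Day 21 (pre-dose), and Day 35". For ECG, "12 lead ECG will be performed at screening (Day -28 to Day -15), Day 1 (pre-dose) and Day 21 (pre-dose".

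**The concern.** Unscheduled values are normally kept out of by-visit means because they come from a selected group at irregular times. That reason does not carry over to a table that asks whether a subject ever crossed a threshold. There, a value obtained because someone was worried about the subject is directly relevant, and it is reasonable to infer (the SAP does not say so) that such values are more likely than routine ones to qualify.

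Safety and tolerability is the trial's secondary objective (Section 3.1.2). If the rule is programmed as written, the Hy's Law row or the clinically significant ECG count could read zero while a qualifying subject sits in a listing. Readers of a study report rely on these counts and would not know that the values had been set aside.

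**Working it through.** The SAP gives no figure on this point, so the main check is textual.

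**1. Is any table exempted from 6.7.5?**

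| Place in SAP | What it provides | Does it admit unscheduled values? |
|---|---|---|
| 6.7.5 | Listings only, no exception | No |
| 10.4, 10.5, 10.6 | Counts by treatment group and visit | Silent |
| Shell 14.3.4.1, repeated for 14.3.4.2, 14.3.4.3 and 14.3.6.2 | Percentages of subjects measured at the corresponding visit | Silent |
| Shell 14.3.5.4 | Subject counts, no visit column, same-visit condition for Hy's Law | Silent |
| 6.1 | Visit labels: "Day 20 and Day 21 as well as End of Study (Follow Up) and Unscheduled" | A label only; assigns nothing to a table |
| Shift-table programming note | Each subject counted once, "in the maximum post-baseline severity, for that laboratory parameter" | Does not mention unscheduled values; belongs to tables titled baseline to Day 21 |

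The last two rows are the nearest counter-texts. Neither says that an unscheduled value enters a summary, and neither concerns the threshold or clinically significant tables. The general rule therefore stands for all of them.

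**2. What the rule does to one case.** Take a subject whose ALT is at least 3 x ULN and bilirubin at least 2 x ULN in a single draw taken between Days 7 and 14 to investigate an adverse event, with both below threshold at every scheduled draw. Under 6.7.5 that draw is listed only. Table 14.3.5.4 counts the subject neither under Hy's Law nor in the ALT and bilirubin rows at those levels. The laboratory count has no row for the value. If the subject also has a qualifying scheduled value, the subject is counted in any case.

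**3. How much the scheduled assessments can see.** This is illustrative; neither onset nor duration is in the SAP. Assume onset uniform over Days 1 to 35 (34 days) and duration d days. Then

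share overlapping a scheduled assessment = sum over gaps of min(d, gap) / 34.

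- Laboratory gaps are 6, 7, 7 and 14 days. d = 2: 8/34 = 24%. d = 3: 12/34 = 35%. d = 5: 20/34 = 59%. d = 7: (6+7+7+7)/34 = 79%. d = 14: 34/34 = 100%.
- ECG has one post-baseline reading, at Day 21, with a gap of 20 days. d = 2: 2/34 = 6%. d = 7: 7/34 = 21%. d = 14: 14/34 = 41%.

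The complement of these shares is not the effect of 6.7.5. The rule acts only on abnormalities that miss the schedule **and** happen to be sampled at an unscheduled assessment:

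effect = (1 - share) x P(unscheduled sample taken).

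The second factor is not in the SAP, so the product cannot be calculated.

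**4. What one subject is worth.** With 31 planned per arm, 1/31 = 3.2 percentage points. With 3 x 31 = 93 in the pooled GSP304 column, 1/93 = 1.1 points.

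**The case against.** The best defence has four parts.

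- **Most of the named tables are by visit.** The counts in Sections 10.4 to 10.6 are defined that way, and leaving unscheduled values out of by-visit rows is ordinary practice. This stands: those rows need no change, and the any-time row is an addition. It does not cover Table 14.3.5.4, nor the fact that the by-visit tables are the only planned counts of such subjects.
- **Nothing is lost from the record.** The values stay in listings. Out-of-range and investigator-flagged laboratory and vital-sign values are listed specifically, and an adverse event under investigation is counted in the adverse-event tables. This stands. A reader might infer from 6.7.5 that all safety summaries are affected; the text reaches only laboratory, ECG and vital-sign summaries.
- **Scheduled-only counts give every arm equal ascertainment.** One arm is open-label, so unscheduled testing could differ by arm. This is a genuine trade-off and needs a footnote, but it does not justify a table that can omit a known case without saying so.
- **Sparse sampling is not uniform.** Vital signs are scheduled often (Day 1 post-dose, Days 2, 7, 14 pre- and post-dose, 20, 21 post-dose, 22 and 35), so the point is weaker there. This also stands.

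**Conclusion.** The point holds as a gap in the rule. Section 6.7.5 has no exception, and read literally it keeps unscheduled and repeat values out of Table 14.3.5.4 and out of the clinically significant counts. A case seen only at an unscheduled assessment would be listed, and possibly reported as an adverse event, but not counted. The conclusion assumes that programmers follow 6.7.5 as written.

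The size is unknown. Each affected subject is worth 3.2 points in a planned arm, but the number of such subjects cannot be derived from the SAP.

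Three stronger readings are tempting and not supported:

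- That the share of transient abnormalities missing a scheduled draw is the share the rule discards. Many would never be sampled at all, and the laboratory coverage above runs from 24% to 100% depending on an assumed duration.
- That no ECG is scheduled after dosing. The Day 21 pre-dose ECG follows earlier doses; what is absent is a scheduled reading soon after a dose. How often ECGs are taken is a design matter, not an SAP error.
- That the same-visit condition for Hy's Law is wrong. Nothing in the SAP shows this. ALT raised at Day 7 with bilirubin raised at Day 14 involves two scheduled draws and has nothing to do with 6.7.5, and that subject still appears in the separate ALT and bilirubin rows.

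**What to change.** - **Section 6.7.5:** confine the exclusion to by-visit descriptive statistics and change-from-baseline summaries.
- **Table 14.3.5.4:** state that all post-baseline values count, scheduled, unscheduled and repeat. Keep the same-visit condition, and say that ALT or AST and bilirubin from the same unscheduled draw can meet it.
- **Tables 14.3.4.1-14.3.4.3, 14.3.6.2 and 14.3.6.5:** add a row for *any time post-baseline, including unscheduled*, and leave the by-visit rows as they are. Amend Sections 10.4 to 10.6 to match.
- **Footnote on each of these tables:** subjects tested more often have more chances to qualify, and the frequency of unscheduled testing may differ for the open-label arm.

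The cost is SAP wording, one extra row in existing shells and the matching programming. No new data are needed and no study procedure changes. The statistical price is the unequal ascertainment that the footnote discloses; the by-visit rows remain available as the scheduled-only comparison.

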### 6.7.6. Pharmacokinetic Parameters

Derivation of PK parameters will be the responsibility of Early Phase, Quantitative Clinical Development (QCD), PAREXEL International and will be conducted either with Phoenix WinNonlin® Professional v. 6.3 (or higher) or SAS® v.9.3 (or higher). The PK parameters in Table 6 will be determined for Tiotropium in plasma after administration of the first dose:

**Table 6: Plasma Pharmacokinetic Parameters (Day 1)**

Parameter	Definition
AUC 0-tau	Area under the concentration-time profile over the dosing interval
C max	Peak concentrations during the dosing interval
t last	Time of last quantifiable concentration
t max	Time of peak drug concentration

The PK parameters in Table 7 will be determined for Tiotropium in plasma following multiple dose administration (Day 21). The terminal elimination half-life will be reported only if data permit a reliable estimation.

**Table 7: Plasma Pharmacokinetic Parameters (Day 21)**

Parameter	Definition
AUC 0-tauSS	Area under the concentration-time profile over the dosing interval at steady state
AUC 0-tauSS/Dose	Dose normalized area under the concentration-time profile over the dosing interval at steady state
C avss	Average concentration during a dosing interval at steady state
C maxSS	Peak concentrations during the dosing interval at steady-state
C maxSS/Dose	Dose normalized peak concentration during the dosing interval at steady state

$C_{minSS}$	Minimum of trough concentrations during the dosing interval at steady-state
$R_{ac}$	Accumulation ratio for $C_{max}$ and $AUC_{0-\tau}$
$t_{1/2}$	Terminal elimination half-life
$t_{last}$	Time of last quantifiable concentration
$t_{max}$	Time of peak drug concentration

The PK parameters in Table 8 will be calculated for Tiotropium Bromide in urine following treatment administration (Day 1 and Day 21):

**Table 8: Urine Pharmacokinetic Parameters (Day 1 and Day 21)**

Parameter	Definition
$A_{etau}$	Cumulative amount of unchanged drug excreted into the urine over the dosing interval
$A_{etau}/Dose$	Dose normalized cumulative amount of unchanged drug excreted into the urine over the dosing interval
Fe%	Fraction of dose (%) excreted into the urine over the dosing interval

#### 6.7.6.1. Handling of Values Below the Limit of Quantification

All plasma/urine concentrations below the lower limit of quantification (LLOQ) or missing data will be labeled as below the limit of quantification (BLQ) or missing, respectively, in the concentration data listings.

#### Considerations in the handling of BLQ data for the generation of plasma PK Parameters and for plotting of individual plasma PK concentration data

BLQ values will be imputed in the PK concentration dataset used for the derivation of PK parameters. The following rules will be applied:

- BLQs at the beginning of a subject profile (ie before the first incidence of a measurable concentration on the first day of dosing) will be assigned to zero;
- BLQs at the end of a subject profile (ie after the last incidence of a measurable concentration on last day of dosing) will be set to missing;
- Single or consecutive BLQs which fall between measurable concentrations will be set to missing.
- Quantifiable concentrations falling between two BLQ values might be set to missing if considered anomalous by the PK Scientist after consultation with the sponsor.

For linear plots, zero concentration value(s) will be included in the plot while missing values will be ignored. For log-linear plots, zero concentration value(s) will be assigned a  $\frac{1}{2}$  LLOQ value with the exception of the pre-dose sample collected on Day 1 while missing concentrations at the end of the profile will be ignored.

